5.4. Data Collection and Management

A trained healthcare professional team will collect and supervise the data collection. Enrolled participants will answer a brief questionnaire focused on recent isoniazid adherence. Patients will be asked to report their recent adherence, including the date of their most recent dose. They will be also asked to estimate how many of the last thirty doses they had missed or how many doses they missed in a typical week and the reasons for any missed doses. Data will be collected from the primary source through interviews and sample urine collection, and a secondary source by a review of the health facility attendance registration book to confirm the patient's medication refill visit attendance. A trained pharmacist and nurses will collect urine specimens in a clean and dry container. Urine collected at any time of the day may be used. The sample does not have to be freshly voided as the sample can be stored at room temperature for 1 to 10 days and thereafter at -20°C and retain its suitability for testing. The urine sample will be collected on day 0, and then after every 2 months i.e., 2 months, 4 months, and 6 months. The urine sample will be discarded immediately after the analysis. A health worker will be trained to administer the EQ-5D. Enrolled patients will be explained the purpose and duration of the study. All participants included in the study provided informed consent and completed the EQ-5D facilitated by the trained health worker in a face-to-face interview at the clinic. The interview will be conducted on the premises of the hospital. Interviews will be conducted at the start of the study, after 2 2-month visits, and then at the end of the study (6th month). To ensure the security of the patients' information, a double-blind randomization technique will be adopted. The computer gives each patient a code number, and the code numbers will then be allocated randomly to the treatment groups. All data will be kept in a database, and backup file with password protectors. All identifiable information will be removed

And replaced by code. Code breaking will be done by the external personnel who are not involved in the study so the biasedness couldn't be possible. At the end of the trial, the patients can check their records on request. The study record shall be destroyed after the research is completed.

5.5. Study End Point:

The study will be ended after 6th month, but still, if the patients are non-adherent to the therapy the study period will be extended to 1 year.

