5.1 Study Design

A longitudinal study design will be adopted to achieve the present study objectives. The study population will be classified with one intervention and one control arm, using a 1:1 allocation ratio, to evaluate whether the intervention is superior to the control treatment will be adopted to achieve the study objectives at General Hospital Penang.

Intervention arm: Enrolled participants will be counseled and educated by a pharmacist on the therapy and benefits of adherence.

Control arm: Enrolled patient will be counseled and educated by the material provided on the therapy and benefits of adherence.

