Subjects can choose to withdraw at any time. Subjects may be withdrawn if the investigator deems that it is detrimental or risky for the subject to continue. As this is a prospective observational study and data in the form of information are only required, the literature suggests about 10-20% dropout or withdrawal has been observed in the past so 20% dropout is already included in the sample size calculation thus the withdrawn subjects will not be replaced with new subjects.

10. Selection of subjects to be included in the analysis

All the subjects who will participate until the end of this study will be included in the final analysis of this study. All subjects who withdraw from the study at any point in time will not be included in the final results analysis.

11. Risk-Benefit Assessment

As stated above, there is no risk from the investigational process and study procedures. No harm could be caused to the patient as there is no invasive procedure involved in the study nor any

Medication is given to the patient. Only non-clinical intervention is given in the study. Study findings shall potentially improve treatment outcomes. The expected benefit outweighs the minimal risk to subjects and thus this study should be supported.

If still any injuries do occur as a direct result of participating in the study, treatment for such injuries shall be provided or paid for by the researcher/ sponsor.

12. Ethics of Study

The study will be conducted in compliance with ethical principles outlined in the Declaration of Helsinki and the Malaysian Good Clinical Practice Guideline.

All aspects of the study protocol, including access to and the use of clinical information of patients, and demographics will get approval by the institutional medical ethics committee locally as well as central health authorities before initiation of this study. Information on individuals will be strictly protected and used for clinical research only.

13. Informed Consent/Assent Process

Patients shall be informed of the study during their usual clinic visits. They will be requested to contact investigators if they are interested. An appointment will be made where the patient information sheet will be provided and explained to them. If they are willing to participate, the consent forms will be signed and dated. If they need to, they are allowed to take the information sheet home to consult with their family members, and another day for getting consent arranged.

14. Conflict of Interest

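### The randomisation is called double-blind and bias is said to be impossible, but patients and the counselling pharmacist know the arm, so self-reported adherence and EQ-5D are unblinded outcomes

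*Combined protocol and SAP*

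**What the plan says.** Section 5.4 says that "a double-blind randomization technique will be adopted". The purpose it gives is "To ensure the security of the patients' information", and the mechanism is that patients receive code numbers and "the code numbers will then be allocated randomly to the treatment groups". It then concludes: "Code breaking will be done by the external personnel who are not involved in the study so the biasedness couldn't be possible". It does not say who is blinded.

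Section 5.1 defines the arms. Intervention: "Enrolled participants will be counseled and educated by a pharmacist on the therapy and benefits of adherence". Control: "Enrolled patient will be counseled and educated by the material provided on the therapy and benefits of adherence". No sham or attention-matched session is described.

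The outcomes in section 5.4 include a patient questionnaire on the last isoniazid dose and on missed doses, and an EQ-5D completed face to face with a trained health worker. There are two less subjective adherence sources: a urine test at months 0, 2, 4 and 6, and the attendance register for refill visits. On the urine test the section says: "A trained pharmacist and nurses will collect urine specimens in a clean and dry container".

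Section 9 (Withdrawal Criteria) describes the design differently again: "As this is a prospective observational study and data in the form of information are only required".

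**The concern.** Double-blinding is a stated property that this comparison cannot have for two of the parties that matter. A patient who has been counselled by a pharmacist knows it, and so does the pharmacist. When the outcome is the patient's own account of missed doses or of health-related quality of life, the patient is in effect the assessor, and knowledge of the arm can shift the answer. Random code numbers and an external code breaker do nothing about this.

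Two things are at stake. Under-reporting of missed doses in the counselled arm, or a more favourable EQ-5D, would look like a benefit of counselling. And a reader who trusts the double-blind label, or the sentence ruling bias out, would not discount for that. The observational label in section 9 adds to the confusion, since section 5.1 allocates patients 1:1 to test superiority.

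**Working it through.** **Reading the sections together**

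1. *Who can be blinded.* From section 5.1, the patient and the counselling pharmacist cannot be. Urine readers and the analyst could be, and interviewers could be kept apart from the counselling, but the protocol provides for none of this.
2. *What the coding does.* Section 5.4 gives it an information-security purpose. It conceals identity in the records, not the counselling from those who took part in it.
3. *Who collects outcomes.* Section 5.4 names a pharmacist among the urine collectors and does not say whether this may be the counselling pharmacist.
4. *Which outcomes are exposed.* Missed-dose self-report and EQ-5D are directly exposed. Urine results and refill attendance are less so, but no primary outcome is named that would rest the adherence comparison on them.

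**How much could it matter?** The protocol has no figure to reproduce here, and the size of the bias cannot be derived from it. The following is an illustration.

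Inputs: n = 191 per arm and two-sided 0.05 (section 6); true non-adherence of 8% or 33% in both arms (the range in section 5.10). Assumptions: no true effect; a two-proportion z-test on self-report; control patients report accurately; counselled patients hide a share r of their non-adherence, with r = 5/33 (about 15%) or 10/33 (about 30%). At 33% non-adherence these shares are 5 and 10 percentage points.

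Let c be the control proportion, t = c(1 − r), d = c − t and p = (c + t)/2. Then SE0 = √[2p(1 − p)/n], SE1 = √[(c(1 − c) + t(1 − t))/n], and

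P(falsely significant benefit) = Φ[(d − 1.96·SE0)/SE1].

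| c | r | t | d | SE0 | SE1 | Argument of Φ | P |
|---|---|---|---|---|---|---|---|
| 0.08 | 5/33 | 0.0679 | 0.0121 | 0.02678 | 0.02677 | −1.51 | 0.066 |
| 0.08 | 10/33 | 0.0558 | 0.0242 | 0.02574 | 0.02571 | −1.02 | 0.154 |
| 0.33 | 5/33 | 0.28 | 0.05 | 0.04711 | 0.04704 | −0.90 | 0.184 |
| 0.33 | 10/33 | 0.23 | 0.10 | 0.04595 | 0.04566 | 0.22 | 0.586 |

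The nominal rate in this direction is 2.5%. Adding the opposite tail (nominal total 5%) raises these values by less than 0.01.

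For EQ-5D, assume a pure reporting shift of b standard deviations. Then P = Φ(b√(n/2) − 1.96) with √(191/2) = 9.77. For b = 0.1, 0.2 and 0.3 this gives about 16%, 50% and 83%. The shifts are assumed; the documents give no EQ-5D variability or expected effect.

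**The case against.** The strongest reply is that adherence does not rest on self-report alone.

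- Section 5.2 has doses taken daily in front of a health worker during the two-month intensive phase, which leaves little room to hide missed doses at month 2. Weekly refill visits follow.
- Section 5.4 checks refill attendance against the register and tests urine at four time points.

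This stands as partial mitigation. It weakens after month 2, when doses are taken at home, and it does nothing for EQ-5D.

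A second reply is that section 5.4 attaches the double-blind label to the randomisation technique and gives data security as its aim, so it may never have been meant as a claim about assessment. That is a fair reading of intent, but the label and the sentence ruling out bias remain, and no one is named as blinded.

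Some stronger readings are tempting but not supported:

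- *That the protocol expressly dismisses expectation bias.* The sentence concerns code breaking and names no type of bias. It is over-confident, not a reasoned exclusion.
- *That the counselling pharmacist, or the same clinical team, collects the outcomes.* Overlap is not barred, but it is not stated either.
- *That the false-positive risk is 59%.* That figure needs the top of the 8–33% range together with the larger assumed share hidden. It also assumes accurate reporting by control patients, who are educated on adherence too, and a binary self-report analysis that the protocol does not name as primary.
- *That nothing can be blinded.* Urine reading and analysis can be.

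**Conclusion.** The point holds as a labelling and blinding-roles fault. The design is not double-blind, the statement that bias is impossible is unsupported, and self-reported missed doses and EQ-5D are unblinded outcomes. The adherence comparison is partly protected by other data sources; EQ-5D is not.

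The size of the bias is unknown. Under the stated assumptions, the probability of a falsely significant adherence benefit is about 7% to 15% at 8% non-adherence and about 18% to 59% at 33%, against a nominal 2.5% in that direction. These figures show sensitivity to differential reporting and are not a forecast. That the label is wrong does not depend on them. The correction should be made, but nothing here shows that the trial's comparison is invalid.

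**What to change.** **Wording.**
- In section 5.4, replace the double-blind description with *randomised, open-label to patients and counsellors, with urine-test reading and analysis blinded to arm*.
- Delete the statement that bias could not be possible.
- In section 9, correct the description of the study as observational.

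**Roles.** State that existing staff other than the counselling pharmacist will collect the code-labelled urine, read the IsoScreen colour without knowing the arm, and conduct the adherence and EQ-5D interviews. This separates the interviews from the counselling but does not make them blinded: patients can disclose their arm, and their own answers remain open to bias whoever asks.

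**Analysis and reporting.** Run the between-arm comparison on coded arms. Report self-reported adherence and EQ-5D as unblinded outcomes, beside the IsoScreen and refill-attendance results. State IsoScreen's limits: it shows recent intake only (the colour table in section 2 refers to 30 hours), and samples are optional (section 5.9). Dosing just before a visit and selectively missing samples could therefore bias it too.

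**Cost.** Protocol wording and a division of tasks among current staff, with no new patients, visits or tests. The small downside is less flexibility in staff assignment.

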3.1 Specific Objectives

1. To perform a systematic review and meta-analysis on evidence-based TB drug adherence.

2. To determine the association between the pharmacist-led intervention and medication adherence level among TB and HIV co-infected patients.
3. To assess the effects of different levels of adherence with therapeutic impact and its possible clinical outcomes.
4. To assess the survival trend with the study population and health-related quality of life (HRQoL) by using the EQ5Dv3 tool.
5. To assess the defaulter patients' approach towards TB and its treatment outcomes.
(Qualitative Approach)

4. Ethical Approval

The study protocols will be approved by the Ethical and Research Committee Ministry of Health, Malaysia. The protocol will also be registered at clinicaltrials.gov

5. Methodology

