5.2 Study Setting

The study will be conducted at Hospital Pulau, Penang from November 2022 to November 2023. We will enroll patients with culture-confirmed TB. Additionally, the enrolled PLHIV with any TB symptoms will be investigated with sputum smear microscopy, mycobacterial culture (BACTEC MGIT), Xpert Ultra, and Chest X-ray (CXR). Patients will be eligible for enrolment if they are ≥ 18 years of age, diagnosed with active TB according to national TB program guidelines, had not been previously treated for these diseases, agreed to start treatment for TB, and could give informed consent in either English or Malay.

In Malaysia, a DOT program has been implemented in two phases, “intensive” and “continuation”. In the intensive phase (daily DOT) the current standard anti-TB regimen recommended by WHO

Consists of a 2-month treatment with INH, rifampicin (RIF), pyrazinamide (PZA), and ethambutol(EMB), followed by a 4-month continuation phase with INH and RIF (2EHRZ/4HR) as daily regimen. In the intensive phase (daily DOT), a patient takes their medication in front of the healthcare worker every day at a health facility. In the continuation phase (non-daily DOT), a patient is given the responsibility to take the medication at home and come to a health facility weekly for health checking and medication refilling.

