5.8 Data Analysis

All analyses were performed using SPSS software, version 28.0 (SPSS Inc., Chicago, IL, USA). *T-test*, $\cong \chi^2$ test, Fisher's exact test, and a logistic regression model were used to determine differences between the intervention group and the control group. According to log-likelihood values, the best fit for the correlation structure was determined to be a compound symmetry structure and random effects were applied to the slope as well as to the intercept. In addition, analysis of variance (ANOVA) was used to determine differences between the two groups based on each monthly accumulated drug adherence rate. Statistical significance was set at $p < 0.05$ (16)

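### Section 5.5 lets non-adherence lengthen the study period without saying for whom. If it applies per patient and outcomes are counted over all follow-up, objectives 3 and 4 compare unequal observation times.

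*Combined protocol and SAP*

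**What the plan says.** - **Follow-up (section 5.5).** The study ends after month 6, but "if the patients are non-adherent to the therapy the study period will be extended to 1 year". Neither the unit of extension (patient or study) nor the time at which non-adherence is judged is given.
- **Visits (section 5.4).** "The urine sample will be collected on day 0, and then after every 2 months i.e., 2 months, 4 months, and 6 months". The last interview comes "and then at the end of the study (6th month"). Nothing is scheduled later.
- **Calendar (section 5.2).** "The study will be conducted at Hospital Pulau, Penang from November 2022 to November 2023", which is 12 months for enrolment and follow-up together.
- **Objectives (section 3.1).** Objective 3: "To assess the effects of different levels of adherence with therapeutic impact and its possible clinical outcomes". Objective 4 begins: "To assess the survival trend with the study population".
- **Analysis (section 5.8).** A t-test, chi-square test, Fisher's exact test and "a logistic regression model were used to determine differences between the intervention group and the control group". ANOVA is added for the two groups' accumulated adherence rates, along with a statement on correlation structure and random effects. No method is named for objective 3, and there is no time-to-event method, person-time, outcome time point or censoring rule.
- **Analysis set (section 10).** "All the subjects who will participate until the end of this study will be included in the final analysis of this study". Anyone who withdraws at any point is left out.

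**The concern.** The trigger for longer observation is non-adherence, and adherence level is the exposure in objective 3. If each non-adherent patient is followed beyond month 6 while adherent patients stop there, a count of deaths, failures, cures or completions by adherence level compares different lengths of time. More time allows more events of any kind, so an association can appear, or a real one can be hidden, because of the follow-up rule alone.

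Section 10 adds a second difference. If the end of the study means month 12 for extended patients and month 6 for the rest, non-adherent patients must stay twice as long to be analysed. One who leaves in months 7-12 would lose even the month-6 data.

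This point concerns observation time and analysis only, not treatment.

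**Working it through.** **Setting the passages side by side.** Section 5.5 allows observation to 1 year; section 5.4 stops at month 6. With a 12-month calendar window, only patients enrolled at its very start can be followed for 12 months. The residence criteria do not reach a year either: 9 months in section 5.6 and six months in section 5.7. No passage sets a horizon for clinical outcomes.

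**Inputs.** From the documents: 382 patients, 191 per arm (section 6); non-adherence of 8-33% (section 5.10); two-sided 0.05. The plan has no figure of its own to reproduce here and gives no event rate. Assumed: a constant hazard *h* of 1%, 2% or 3% per month, equal in adherent and non-adherent patients (no true effect), and uniform enrolment over the first 6 months. A patient extended until the window closes then has between 6 and 12 months of follow-up.

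**Step 1: per-patient extension, non-adherence known independently of events.** Risk by time *t* is F(t) = 1 - exp(-ht). Adherent patients have risk F(6). Extended patients have the mean of F(t) for t uniform on 6 to 12, which is 1 - [exp(-6h) - exp(-12h)]/(6h).

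| h per month | F(6) | Extended, cut at window | Ratio | F(12) | F(12)/F(6) |
|---|---|---|---|---|---|
| 0.01 | 0.058 | 0.086 | 1.48 | 0.113 | 1.94 |
| 0.02 | 0.113 | 0.164 | 1.45 | 0.213 | 1.89 |
| 0.03 | 0.165 | 0.236 | 1.43 | 0.302 | 1.84 |

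The last column needs every extended patient to reach 12 months, which the calendar does not allow.

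**Step 2: false positives by adherence class.** Simulated two-proportion test, 382 patients, follow-up cut at the window, for h = 0.01, 0.02, 0.03:

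- 8% non-adherent (31 v 351): about 13%, 16%, 20%.
- 33% non-adherent (126 v 256): about 18%, 29%, 39%.
- Common month-6 horizon: 4-5% throughout.

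**Step 3: non-adherence judged at month 6.** Only patients event-free at month 6 can be extended, and earlier events fall in the non-extended group. If a share *p* of event-free patients is extended, the non-extended risk is F(6)/[F(6) + (1 - p)exp(-6h)]. The extended risk is F(6) with a full further 6 months, or 1 - [1 - exp(-6h)]/(6h) when cut at the window. At h = 0.02 and p = 0.20:

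- Non-extended risk: 0.113/(0.113 + 0.80 × 0.887) = 0.138.
- Extended risk: 0.113 (full) or 0.058 (cut).
- Ratio: 0.82 or 0.42.

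Over h = 0.01-0.03 and p = 0.08-0.33 the ratio is 0.69-0.93 (full) or 0.35-0.48 (cut). The direction reverses.

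**Step 4: arm comparison.** Each arm's risk is p × (extended risk) + (1 - p) × F(6), with 191 per arm and no true effect. At an extreme split of 33% v 8% non-adherent, the ratio is 1.10-1.12 and false positives are 6-7% with follow-up cut at the window (1.20-1.22 and 8-14% with full 12 months). At an assumed 25% v 15%, false positives are 5-6% (6-7% full).

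**The case against.** The strongest reply is that section 5.5 speaks of the study period and of patients in the plural, which is study-level wording. If the whole study is extended, adherence does not set any patient's observation time and this bias does not arise. That stands: the per-patient reading is natural, because adherence is measured patient by patient, but the text does not settle it.

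A second reply is that bias also requires outcomes to be pooled over all available follow-up. All scheduled urine tests and interviews fall by month 6, and the regimen in section 5.2 lasts 2 + 4 months, so outcomes at month 6 are a fair reading too. That also stands, but the plan does not say it.

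Third, the hazards and accrual pattern are assumed, and the ratios run from 0.35 to 1.94 across scenarios. They show that the problem can matter, not how large it would be here.

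A reader might infer more than the documents support:

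- **That objective 3 is biased as written.** This needs both the per-patient reading and pooling over all follow-up.
- **That the risk ratio would be near 2.** This needs full 12-month follow-up, which the calendar window excludes for nearly all patients.
- **That the randomised comparison is undermined.** Step 4 shows only a small effect unless the arms differ greatly in non-adherence and follow-up is complete.
- **That adherence and EQ-5D results are distorted.** At the scheduled visits up to month 6 the extension itself does not affect them.

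**Conclusion.** The point holds in conditional form. What the documents establish is an ambiguous extension rule tied to adherence, a conflict between it and both section 5.4 and the calendar window, and no stated horizon or censoring rule for clinical outcomes. If the extension is per patient and outcomes are counted over all follow-up, objectives 3 and 4 could report an adherence association with no true effect. Under the assumed hazards and accrual, the size is a risk ratio of about 1.4-1.5 and a false-positive rate of about 13-39%, with the direction reversed if non-adherence is judged at month 6.

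This should be corrected, but it bears mainly on non-randomised objectives. Confidence is medium, because the size rests on assumptions that the plan cannot confirm.

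**What to change.** 1. In sections 5.5 and 5.8, state that comparisons of clinical outcomes by arm and by adherence level use a common month-6 horizon for every patient, with survival censored at month 6 and later data reported descriptively.
2. In section 10, define the end of the study as month 6, so that leaving in months 7-12 does not remove month-6 data.
3. In section 5.5, state whether the extension is per patient or study-wide and when non-adherence is judged. Reconcile it with the visit schedule in section 5.4 and the November 2022 to November 2023 window.
4. As an option for objective 3, name a model with time-varying adherence.

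The cost is wording only: events after month 6 move to a descriptive table, and no patients or visits are added. The common horizon removes the unequal observation time. It does not remove confounding, because adherence is not randomised.
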